13 DATA ANALYSIS

13.1 Statistical and Analytical Plans

A formal Statistical Analysis Plan (SAP) will include all statistical strategies and details necessary for performing the interim and final analyses.

13.2 Statistical Hypotheses

Co-Primary Endpoint I

The hypothesis test is designed to show superiority of Edwards Cardioband System (Device group) to Control group for the primary endpoint via the chi-square statistic, for the difference in the prevalence of MR \leq 2+ at one year, with a two-sided alpha of 0.05. The null (H_0) and alternative (H_A) hypotheses are:

$$H_0$$
: $P_{CardB}(T) - P_{Control}(T) = 0$

$$H_A$$
: $P_{CardB}(T) - P_{Control}(T) \neq 0$.

 P_{CardB} and $P_{Control}$ are the estimates of the prevalence of MR \leq 2+ at T=one year in the Device and Control groups, respectively.

Co-Primary Endpoint II

The hypothesis test is designed to show superiority of Edwards Cardioband System (Device group) to Control group for the hierarchical sequence of the components of the co-primary endpoint, as analyzed via the Finkelstein Schoenfeld test. The Finkelstein-Schoenfeld test is a Generalized Gehan Wilcoxon (GGW) test. See section on primary endpoint analysis for details.

The null hypothesis is that none of the components in the hierarchy are improved by the treatment whereas the alternative hypothesis is that at least one of the components are improved by the treatment.

13.3 Analysis Populations

13.3.1 Enrolled Population

Any patient who has signed informed consent will be included as part of the Enrolled Population. Should a patient be considered ineligible after signing consent and before randomization, the reason for failure will be documented, and the patient will be exited

from the study. Serious adverse events (SAEs) will be reported for all enrolled patients through study exit.

13.3.2 Intent-to-Treat (ITT) Population – for safety analysis

The Intent-to-Treat population (ITT) [full analysis set (FAS)] will consist of all patients who have signed informed consent and have been randomized.

Patients that have entered the procedure room but have not received an implant attempt (passing of any Edwards Cardioband System component past the skin) will be deregistered and followed through 30 days for safety purposes only.

13.3.3 Modified Intent-to-Treat population (mITT) - for efficacy analysis

The Modified Intent-to-Treat population (mITT) will consist of all patients randomized to the Control Group and all patients randomized to the Edwards Cardioband System (Device Group) that have had the Edwards Cardioband System implanted. The mITT population represents the Primary Analysis population for this study. The randomization will continue until 375 mITT patients are enrolled.

A separate summary of the safety on all screen failure patients shall be provided as part of the study final report.

13.3.4 Device Implant Population

The Device Implant population is defined as the subset of the mITT population consisting of those patients for whom any part of the Edwards Cardioband System is implanted and remains in position (i.e., absence of any anchor detachment). This population will be utilized as a secondary analysis population.

13.4 Statistical Methods

13.4.1 General Approach

All data collected will be summarized overall and by treatment groups.

For continuous variables (e.g., age, percent diameter stenosis, and lesion length), results within treatment group will be summarized with the numbers of observations, means, medians, standard deviations, 25th and 75th percentiles, minimums, and maximums per the table mockups. Differences between the treatment groups, where specified, will be summarized with the differences of the two means, 95% confidence intervals for

the difference between the means, and p-values based on a t-test. The distributions within each group will be tested for normality using the Shapiro-Wilks test and if normality cannot be assumed then a Wilcoxon rank-sum test and 95% confidence interval of the median will be presented. The confidence interval for the difference of two means will be calculated under the assumption of unequal variances.

For categorical variables such as gender, in-hospital event rates, and angina status, results within treatment group will be summarized with patient counts and percentages. Differences between the two treatment groups, where specified, will be summarized with the difference in percentages, the asymptotic 95% confidence interval for the difference of two percentages, and a p-value based on a chi-squared test. If 20% or more of the expected cell frequencies are less than 5, a Fisher's exact test will be used to test for differences in proportions.

For the determination of event rates in-hospital, the number of all patients in the patient population will be used as the denominator. For variables ascertained at followup, the denominator will be only those patients who had follow-up performed at that time point. Unless otherwise noted, patients with missing data are excluded from the denominator.

Survival analysis techniques will be used to analyze the time-to-event variables. Patients without events will be censored at their last known event-free time point. If this event-free time point occurs after the analysis time point, the days to event variable will be set equal to the analysis time point so that the patient will be included in the analysis. For patients who did not have an event or early withdrawal and have not yet completed the analysis visit, they will be censored at the time of their last follow-up. Time to first event curves will be constructed using Kaplan-Meier estimates and all post discharge results will be summarized with Kaplan-Meier estimates of event rates. Hazard ratios, confidence interval for the hazard ratios, and p-values may also be presented from a Cox proportional hazards model.

Covariate analyses and the variables of interest, as well as possible subgroup analyses of interest, will be pre-specified in the study SAP.

13.4.2 Analysis of the Primary Endpoints (Efficacy)

The co-primary endpoints will be analyzed in a hierarchical order where endpoint I must meet statistical significance in order to proceed to endpoint II. This approach does not require any adjustment for multiplicity.

Co-primary endpoint I

The proportion of patients who meet the criteria for reduction of mitral regurgitation $(MR \le 2+)$ at one year follow-up.

The comparison of co-primary endpoint I between Device and Control groups will be performed using a Chi-Square-test for two independent proportions.

Co-primary endpoint II

Conditional on the first co-primary endpoint meeting statistical significance, co-primary endpoint II will be analyzed using the non-parametric method described by Finkelstein and Schoenfeld. Briefly, each patient pair is compared in descending order of the endpoints until one member of the pair shows superiority. As specified above, these endpoints are:

- 1. Time to all-cause death within the first year
- 2. Number of heart failure hospitalizations within the first year
- 3. Improvement of 6-Minute Walk Test at one year vs. baseline (≥ 40 meters improvement)
- 4. Improvement in Kansas City Cardiomyopathy Questionnaire (KCCQ) score at one year vs. baseline (≥10 point improvement).

The specifics of the procedure will be provided in greater detail within the statistical analysis plan (SAP).

The Finkelstein-Schoenfeld method starts by a comparative outcome assessment for all patient pairs. While the example comparison given in the table below shows a Device patient being compared to a Control patient it should be noted that a pairwise comparison is made for every patient versus every other patient.

Comparison of each potential patient pair	How Event is
(e.g. 1 from Device group and 1 from Control group)	Assessed
Step 1	
If 1 or both patients die due to all-cause	
Patient in Device group dies first due to all-cause	Favors Control
Patient in Control group dies first due to all-cause	Favors Device
Both patients die on the same day due to all-cause	Go to Step 2
If neither of the patients die due to all-cause	Go to Step 2

Comparison of each potential patient pair	How Event is
(e.g. 1 from Device group and 1 from Control group)	Assessed
Step 2	
If no ranking yet available	
Patient in Device group had more hospitalizations** for HF	Favors Control
Patient in Control group had more hospitalizations** for HF	Favors Device
Both patients were hospitalized** equal number of times	Go to Step 3
Step 3	
If no ranking yet available	
Patient in Device group but not patient in Control group	Favors Device
improved 6 minutes walking distance ≥ 40 meters compared to	
baseline	
Patient in Control group but not patient in Device group	Favors Control
improved 6 minutes walking distance ≥ 40 meters compared to	
baseline	
Both patients improved 6 minutes walking distance ≥ 40	Go to step 4
meters compared to baseline	
Neither of the patients improved 6 minutes walking distance ≥	Go to step 4
40 meters compared to baseline	
Step 4	
If no ranking yet available	
Patient in Device group (but not control) improved KCCQ score	Favors Device
≥10 points compared to baseline	
Patient in control group (but not device)improved KCCQ score	Favors Control
≥10 points compared to baseline	
Both patients improved KCCQ score ≥10 points compared to	Tie
baseline	
None of the patients improved KCCQ score ≥10 points	Tie
compared to baseline	

^{**} Only hospitalizations for heart failure are counted

The following rules are applied with the pairwise comparative outcome assessment:

- If any one of the patients in a patient pair is missing data for a variable included in the hierarchy then the pair will be considered a tie in regards to that variable/level and will proceed to the next level in the hierarchy.
- The time dependent events are censored at exactly 1 year after randomization.
- Patients who are censored during the first year (includes patients who are lost to follow-up as well as patients who die) will be compared to other patients using available data up until the time at which the patient was censored. In other words,

PROTOCOL NUMBER: 2017-05

the number of heart failure hospitalizations up until the censoring time will be compared between the patient pair.

- Inclusion of hospitalizations is based on adjudication by the Clinical Events Committee (CEC).
- The index hospitalization for Edwards Cardioband System implant in patients randomized to Device group is not counted as heart failure related hospitalization. However, if the hospital stay is prolonged beyond 5 days because of a heart failure complication, it is counted as a HF-related hospitalization. This rule is also applies to surgical mitral annuloplasty or replacement that are performed during follow-up in patients randomized to Control.
- Hospitalizations beginning prior to the exact 1 year time point are counted for analysis of frequency of hospitalization.
- The 6MWT and KCCQ data from the 1-year visit are used regardless of whether the visit is before or after the exact 1 year time point.
- If clinical follow-up of one or both patients is censored, the pairwise outcome assessment is performed on the basis of those events that occurred during the smaller of the two follow-up times. Specifically, if a Control patient experiences an event on a particular day, and the Device patient is censored on that day or a later day, then the pair favors Device.

Details of the pairwise comparative outcome assessment process with full scenario analyses are provided in the Statistical Analysis Plan (SAP).

The Finkelstein-Schoenfeld test statistic is a Generalized Gehan Wilcoxon (GGW) test that requires information about the pairwise outcome assessment of all pairwise comparisons, including those within the Device and Control groups.²⁹

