1.4 Prior Clinical Experience with the Edwards Cardioband System

The Edwards Cardioband System received CE Mark in September 2015. The CE Mark was based on the results of a prospective multicenter clinical trial conducted in Europe. This trial of patients demonstrated the safety and effectiveness of Edwards Cardioband System in mitral annular reduction as a highly effective first-line treatment option for reducing mitral regurgitation (MR) and improving quality of life scores. The Edwards Cardioband System was shown to significantly reduce annular size, with significant improvement in MR acutely, at 6- and 12- months. 23,24 Study patients will be followed for a total duration of years and is currently ongoing with the last patient reaching the follow up in .

Based on the encouraging experience to date, Edwards Lifesciences believes that a multicenter, prospective, randomized pivotal clinical trial for treatment of functional mitral regurgitation is reasonable and warranted.

[figure not shown]
2 Device Description

Edwards Cardioband System ACTIVE Pivotal Clinical Trial PROTOCOL NUMBER: 2017-05

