5 STUDY ENDPOINTS

5.1 Co-Primary Efficacy Endpoints (evaluated at 1 year)

- Co-primary endpoint I:
 - 1. Prevalence of MR \leq 2+ at one year.
- Co-primary endpoint II:

Hierarchical comparison between the Device and Control groups using Finkelstein-Schoenfeld methodology:

- 1. Time to all cause death
- 2. Number of heart failure hospitalizations
- 3. Improvement in 6 Minute Walk Test (6MWT) vs. baseline (≥ 40 meters improvement)
- Improvement in Kansas City Cardiomyopathy Questionnaire (KCCQ) at one year vs. baseline (≥ 10 points improvement)

The co-primary endpoints will be analyzed in a hierarchical order where the co-primary endpoint I must meet statistical significance in order to proceed to co-primary endpoint II. This approach does not require any adjustment for multiplicity. The co-primary efficacy endpoints were chosen in order to capture the ability of the Edwards Cardioband System to effectively reduce MR (co-primary endpoint I) as well as its ability to improve clinical outcomes through reducing MR (co-primary endpoint II).

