5.3 Secondary Safety Endpoints (through 30 Days) [Device Group only]

- 1. Death
- 2. Stroke
- 3. Myocardial infarction
- 4. Pericardial effusion requiring drainage
- 5. Mitral valve reintervention
- 6. Access site and vascular complications requiring intervention
- 7. Left circumflex coronary artery injury requiring intervention
- 8. Need for a new permanent pacemaker

5.4 Secondary Endpoints through 1 Year (Powered):

The following key secondary efficacy endpoints will be tested in comparison to control in a hierarchical order to preserve statistical power.

- 1. MR ≤ 1+
- 2. NYHA Class
- 3. Kansas City Cardiomyopathy Questionnaire (KCCQ)
- 4. 6 Minute Walk Test (6MWT)
- 5. SF-36v2 Health Survey (SF-36)
- 6. Heart Failure Hospitalizations
- 7. Cardiovascular mortality
- 8. All-cause mortality

5.5 Other Secondary Endpoints:

The following outcomes will be assessed for device and control, where appropriate:

For the Device Arm:

1. Device Success (measured at 30 days): Device is deployed as intended and the delivery system is successfully retrieved as intended at the time of the patient's exit from the cardiac catheterization laboratory (per device analysis).

- 2. Procedural Success (measured at 30 days): Device success with evidence of MR reduction ≤ MR2+ at discharge and without the need for a surgical or percutaneous intervention prior to hospital discharge (per patient analysis).
- 3. Clinical Success (measured at 30 days): Procedural success with evidence of MR reduction ≤ MR2+ and without MAEs* at 30 days (per patient analysis).
 - *Major adverse events (MAE) defined as death, stroke, myocardial infarction, pericardial effusion requiring drainage, left circumflex coronary artery injury requiring intervention, mitral valve reintervention and access site and vascular complications requiring intervention.
- 4. Responder analysis percentage of patients who achieve:
 - a. $MR \le 2+$, and
 - b. Meets at least two of the following criteria:
 - Improvement vs. Baseline in Symptoms (e.g., NYHA Class improvement ≥
 - Improvement vs. Baseline in Functional Status (6MWD improvement ≥ 30 ii. meters)
 - Improvement vs. baseline in QoL (KCCQ improvement ≥ 5 points) iii.

For both the Device and Control Arms:

- 1. Patient success (measured at 1 year) is defined as
 - a. Patient remains alive and stroke free, and
 - b. No re-hospitalizations (or equivalents) for HF, and
 - c. Patient meets at least two of the following criteria:

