12.2 Data Collection & Follow-Up for Discontinued/Withdrawn Patients

All randomized patients are considered eligible for the assigned treatment and protocol defined follow-up and will be required to adhere to the assessment schedule outlined in Table 4. Patients may withdraw at any time from the clinical study without jeopardy or prejudice. If a patient terminates from the study, the reason for study termination will be recorded. If termination is a result of an adverse event or death, an Adverse Event eCRF will also be completed. Patients who withdraw consent after treatment will not be required to undergo follow-up after withdrawal, but will still be considered part of the patient cohort.

Every attempt will be made to conduct an exit/final visit prior to a patient terminating from the study. The reason for early discontinuation/termination will be documented in the source documents and eCRFs.

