### 7. SUMMARY OF BASELINE INFORMATION

### 7.1 Patient Enrollment and Accountability

The patient enrollment table will include both ITT and mITT populations. Patients from each site will be summarized separately. The patient disposition table will include total number of patients divided into the following categories: visit not yet due, death, explant, withdrew from study, lost to FU, visit completed, and visit not performed. Patients are considered eligible for follow-up if their visit window is open and prior to FU visit window, they are alive, not explanted, did not withdraw from study, and are not lost to FU. Each follow-up visit will have its own disposition section.

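### Co-primary I takes the one-year MR grade as observed, so MR lowered by a later mitral procedure is credited to the assigned arm, and an explanted Device patient who is not scanned drops out instead of counting as a failure

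*Protocol*

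**What the plan says.** Co-primary endpoint I is "The proportion of patients who meet the criteria for reduction of mitral regurgitation" (MR ≤ 2+) at one year, and the comparison is "performed using a Chi-Square-test for two independent proportions" (Protocol 13.4.2). Protocol 5.1 and SAP 3.3 and 8.1 define it the same way. The first gated secondary endpoint, MR ≤ 1+ (Protocol 13.4.4, SAP 8.4a), has the same form. None of these sections says how to score a patient who had a mitral procedure, an explant or a transplant before the one-year echo. Protocol 5.1 states the purpose: the endpoint was "chosen in order to capture the ability of the Edwards Cardioband System to effectively reduce MR".

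The plan expects such events. Table 7 in Protocol Appendix A lists device explantation, a second transcatheter mitral repair device and a surgical annuloplasty device among anticipated events. The pairwise rules for co-primary II mention "surgical mitral annuloplasty or replacement that are performed during follow-up in patients randomized to Control", but only for counting heart failure hospitalizations. Procedural Success (Protocol 5.5) does carry a condition of this kind: MR reduction must be achieved "without the need for a surgical or percutaneous intervention prior to hospital discharge".

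On follow-up, SAP 7.1 treats patients as eligible for a visit if, before its window, "they are alive, not explanted, did not withdraw from study, and are not lost to FU". Protocol 12.2 says: "All randomized patients are considered eligible for the assigned treatment and protocol defined follow-up". SAP 6.1 takes as denominator only patients with follow-up at that time point, and SAP 6.2 imputes nothing. SAP 10 declares a single difference from the protocol, the enrolled definition for roll-in patients.

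**The concern.** The endpoint is meant to show what the band does to MR, but the scoring records what the valve looks like at one year, whatever was done to it in between. A band that failed and was followed by valve surgery is credited to the device, and a Control patient who had a mitral procedure is credited to medical therapy alone.

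The explant wording adds a second route that only the Device arm can take. An explanted patient belongs to the mITT population, because the band was implanted. If the SAP 7.1 rule means the one-year echo is not done, the patient leaves the denominator. If the echo is done, the observed grade counts. Explant is not a failure in either case.

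What is at stake is the meaning and size of the reported MR rates for co-primary I and for MR ≤ 1+.

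**Working it through.** **The plan's own figure.** Protocol 13.5 and SAP 8.11 assume 375 patients at 2:1, 10% against 70%, two-sided alpha 0.05 and data for 60%. That gives 0.6 × 250 = 150 Device and 0.6 × 125 = 75 Control patients. The pooled proportion is (105 + 7.5)/225 = 0.50.

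- Null SE = √[0.25 × (1/150 + 1/75)] = 0.0707.
- Alternative SE = √(0.7 × 0.3/150 + 0.1 × 0.9/75) = 0.0510.
- z = (0.60 − 1.96 × 0.0707)/0.0510 ≈ 9.0, so power exceeds 99.9% and the stated >99% is reproduced.

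**Scoring as written**

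| History before the one-year echo | Scored under the plan |
|---|---|
| Device, band fails, mitral surgery or another mitral device, MR ≤ 2+ | Device success |
| Control, mitral procedure, MR ≤ 2+ | Control success |
| Transplant in either arm, MR ≤ 2+ | Success of that arm |
| Device, explanted, no echo | Not in the denominator |
| Device, explanted, echo done | Whatever grade is seen |

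**Size in the Device arm.** The documents give no rescue or explant rates, so 8 patients of each kind are assumed. The reported rate is 105/150 = 70.0%.

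- 8 of the 105 successes due to another procedure: 97/150 = 64.7%.
- 8 further implants explanted and dropped: 105/158 = 66.5%.
- Both: 97/158 = 61.4%, which is 8.6 points below the reported rate.

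The synopsis instead assumes up to 20% attrition (200 Device patients evaluable). The same counts then give 132/200 = 66.0%, 140/208 = 67.3% and 132/208 = 63.5%.

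**Control arm.** Four rescued patients of 75 on top of 10% unaided: (7.5 + 4)/75 = 15.3%.

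**Net effect on the difference**

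- 8 Device and 4 Control rescues, no explants: reported 105/150 − 11.5/75 = 54.7 points; corrected 97/150 − 7.5/75 = 54.7 points. The bias is zero.
- Adding 8 dropped explants: corrected 97/158 − 10% = 51.4 points, so the report is 3.3 points too high.

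**Range.** With a reported 70%, rescue share r of that rate and explant share e, the corrected Device rate is (0.70 − r)(1 − e).

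| e | r = 0 | r = 5 points | r = 10 points |
|---|---|---|---|
| 2% | 68.6% | 63.7% | 58.8% |
| 5% | 66.5% | 61.75% | 57.0% |
| 10% | 63.0% | 58.5% | 54.0% |

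At the far corner with Control unchanged at 10%, the difference is 44 points instead of 60. In the other direction, rescue of 5%, 10% or 20% of Controls, all scored as successes on top of 10% unaided, raises the Control rate to 0.10 + 0.9 × rescue = 14.5%, 19.0% or 28.0%. The reported difference from 70% falls to 55.5, 51.0 or 42.0 points. Power stays above 99.9% throughout.

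**The case against.** Scoring the grade as observed is a recognised treatment-policy choice, and a composite failure rule is a different estimand rather than a correction. That would be a full answer if the plan said so. It does not: Protocol 5.1 states a device-specific purpose, and a treatment-policy analysis needs explanted patients to be followed, which SAP 7.1 undercuts.

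The events may also be few. Planned mitral procedures and cardiac surgery planned within 12 months are exclusions, Controls may cross over to Cardioband only after the one-year assessment, and the protocol's background describes surgery for functional MR as limited to a small group. This stands, and it is why the sizes above are illustrations.

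SAP 7.1 governs a disposition table and does not itself cancel an echo. That stands too: the loss of explants arises only when it is combined with the SAP 6.1 denominator and no imputation. Protocol 13.6 promises multiple imputation and tipping-point analyses, but SAP 6.2 does not carry them forward. The Echo protocol and CEC Charter are not among the documents and might hold a scoring rule.

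The documents do not support some stronger readings that a reader might infer:

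- *Explants also remove deaths and heart failure hospitalizations from co-primary II.* The pairwise rules do not name explant as censoring, and the SAP 5.1 last information date draws on any source, including adverse events.
- *Controls may get the band outside the trial, because* "The Edwards Cardioband System received CE Mark in September 2015" *and European sites may enrol.* Nothing in the documents points to such use.
- *Mitral interventions are recorded only in years 2 to 5.* The headings can be read as cumulative, though SAP 3.9 speaks of yearly collection at 2 to 5 years, and adverse events are collected from consent.
- *LVAD belongs with the mitral procedures.* It is not a mitral procedure, and the documents give no ground for scoring it as an MR failure.

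**Conclusion.** The point holds for the two MR endpoints. As written, a Device failure can end as a success (after another procedure) or as missing (after explant without an echo). Neither fits the stated purpose of co-primary I. SAP 7.1 contradicts Protocol 12.2, and SAP 10 does not declare this.

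The size depends wholly on assumed rates. With 8 rescues and 8 explants against 150 evaluable patients, the Device rate is overstated by up to 8.6 points. A reader might infer that the treatment difference is overstated by as much. That does not follow, because Control rescue acts in the opposite direction; the net bias is unknown and may be zero. Nor is the gate to co-primary II at risk, since power exceeds 99% under every assumption tried. The issue is how to interpret the reported rates and their difference. It should be fixed before the analysis, but it does not threaten the significance test.

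**What to change.** In SAP 8.1 and 8.4a (and Protocol 13.4.2 and 13.4.4), state that any patient in either arm who had mitral surgery, another transcatheter mitral procedure, explant or transplant before the one-year echo is scored as not meeting the MR criterion and stays in the denominator. Report the observed-grade analysis as a sensitivity analysis.

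Reconcile SAP 7.1 with Protocol 12.2 by removing the explant condition from the follow-up eligibility rule, or else declare the difference in SAP 10. With the scoring rule above, explanted patients count as failures whether or not they are scanned. Tabulate these interventions by arm from randomization, and clarify the timing wording in SAP 3.9.

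The cost is SAP wording and one derived flag, built from procedures that should already reach the database through adverse-event and hospitalization reporting. The Device MR rate may read slightly less favourably.
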